6.1.4 INVESTIGATION OF ENDPOINTS

The trial relevant data has to be recorded in time in the electronic CRF. The use of the eCRF (MACRO 4) makes it possible to provide the raw data in CDISC readable standard. Electronic data of EIT, CT-, MRI-images, ultrasound assessments and radiographs, only marked with the subject identification number, will also be transferred to the KKS cloud in patient specific folders.

6.1.5 STUDY RELEVANT DEVICES

The serial numbers of all used devices will be documented in the respective ISF and the TMF.

The recording of the measurements will be pseudonymised.

- PulmoVista 500: This is a device that can measure and visualize global and regional impedance among a cross-section of a patient's thorax. The device uses very low alternating currents administered to the patient's chest through an electrode belt. The measurement is non-invasive, radiation free and yields results in real time (see above 2.4).
- Ventilator: A standard patient ventilator with a compatible data interface to PulmoVista 500 (e.g. Draeger V500 or Evita XL) to allow recording of ventilation data by PulmoVista 500 .
- Laptop: Standard laptop computer running software (Synology Cloud Station Drive, respective current version) to transfer data from PulmoVista 500 to the KKS cloud (imbcloud.medizin.tu-dresden.de).
- USB-Flashdrive to transfer the data determined during measurements to the statistician via laptop and KKS cloud (see above and below Datamanagement). Access to the Flashdrive reserved to specially authorised users.

6.1.6 PROCEDURES TO REPLACE PARTICIPANTS

As this study does not have treatment arms, replacement of participants is not necessary. The calculated sample size includes a safety margin for dropouts.

6.2 CONCOMITTANT MEDICAL MANOUVERS

The medical care of the patient will not be altered by this purely observational trial. We do however capture data while medical care is being altered (e.g. changes in ventilator settings), but these changes are in no way affected by the study protocol.

6.2.1 EXPOSITION TO MEDICAL DEVICE

All devices are approved acc. Medical Device Act and will be used accordingly.

Measurement with PulmoVista 500 during ventilation shall last for a maximum of eight hours.

6.2.2 USE OF MEDICAL DEVICE

All devices are used according to their intended purpose according to the user manuals and the standard training of the users ("Geräteeinweisung").

6.3 PARTICIPANTS

6.3.1 INCLUSION CRITERIA

A potential subject will be included in the study if he/she meets all of the following inclusion criteria:

- Male and female patients (18 years of age or older),
- On respiratory support in ICU care or scheduled for such (e.g. postoperatively) or scheduled for surgery with OLV
- Patients of which the monitoring of ventilation distribution may be of clinical interest,
- Patients being ventilated via an artificial airway with a mechanical ventilator that is compatible with PulmoVista 500
- Patients scheduled for changes in ventilation settings that may cause relevant changes in the ventilation
- Chest circumference between 70 and 150 cm,
- Written informed consent to participate in the study provided by either the patient or the legal representative of the patient.

6.3.2 EXCLUSION CRITERIA

A potential subject will be excluded from the study if he/she meets any of the following criteria:

- Currently has a permanent or temporary pacemaker, implantable cardiac device (ICD) or other device emitting electrical energy,
- Has a BMI ≥ 50 ,
- Has a tidal volume (V_T) ≤ 200 mL,
- Current uncontrolled body movements such as tics, tremors or seizures,
- Current wound dressings or infections on the chest that might interfere with the electrode belt placement,
- Women of child bearing potential whose pregnancy cannot be excluded based on a pregnancy test or other proven facts.
- Allergic to materials used in the electrode belt,
- Participation of the patient in an interventional trial within the last four weeks before enrollment in this trial

- Evidence suggesting that the patient or his legal representative is not likely to follow the trial protocol (e.g. lacking compliance),
- infectious diseases that require isolation of patient (e.g. MRSA),
- Concomitant use of an air anti-decubitus medical mattress with dynamic inflation that cannot be deactivated during EIT measurements.

6.3.3 POPULATION AND INDICATION

- Intensive care unit (ICU) patients, who are mechanically ventilated via an artificial airway (endotracheal tube or tracheostomy cannula) and who are expected to be subjected to major changes in their ventilator settings will be monitored with the PulmoVista 500 device before, during and after the changes. These changes in the ventilator settings should result in recognizable changes in the distribution of ventilation in the lungs.

Examples of such interventions are:

- Spontaneous breathing trial (SBT) using the ventilator (as opposed to SBT using a T-piece)
- Switching between different modes of ventilation (e.g. volume controlled, pressure controlled, pressure support, CPAP)
- Initial adjustment of ventilation after ICU admission
- Weaning of ventilation in preparation of extubation
- PEEP trials and recruitment maneuvers
- Suctioning maneuvers

- Patients who are scheduled for surgeries that require blocking of one bronchus (e.g. one-lung-ventilation by insertion of a double lumen tube or bronchial blocker)

6.3.4 DURATION AND TIMELINES OF THE CLINICAL INVESTIGATION

Successful enrollment of the entire study cohort is expected to be completed within 12 months.

6.3.5 DURATION PER PARTICIPANT

Data acquisition per patient is anticipated to be completed within eight hours. Additional patients will be evaluated for any adverse events on day 1, 2 or 3 after the study day. No further follow up for the purposes of the clinical study is required.

6.3.6 NUMBER OF PARTICIPANTS

A sample size of n=80 patients (including at least 25 patients with OLV) has been calculated with an assumed drop-out rate of 15%.

6.3.7 RECRUITING TIMELINE

Recruiting time (FPFV – LPFV): 01/2017 – 09/2017

6.4 STUDY PROCEDURES

6.4.1 VISIT 1 - SCREENING AND INFORMED CONSENT

Patients are considered "enrolled" when written informed consent has been obtained and all in- and exclusion criteria are appropriately met.

6.4.1.1 PATIENTS WHO ARE NOT YET ADMITTED TO ICU

Patients who are not yet admitted to ICU will be screened preoperatively, e.g. during the preoperative evaluation by the anesthesiologist. The physicians responsible for the patients' medical care will inform the study team when the actual medical intervention is planned. Study personnel will have a screening checklist to identify patients who might be eligible to participate (e.g. scheduled for thoracic surgery or patients who are scheduled for major surgery that most likely requires postoperative sedation and weaning in the ICU).

If patients confirm interest in participating in this study, investigator will evaluate inclusion and exclusion criteria according to the checklist. If all in- and exclusion criteria are appropriate, investigator will explain the study protocol to the patient and obtain written consent.

6.4.1.2 PATIENTS WHO ARE ALREADY IN THE ICU

Patients who are already in the ICU will be screened by study personnel by interviewing the physicians responsible for patient care in the ICU. Study personnel will use a checklist to determine if a patient is expected to undergo a change in ventilation situation that is appropriate for inclusion in the study (e.g. spontaneous breathing trial, changes in PEEP settings). Study personnel will then approach the patients' legal representative (e.g. person in charge to explain the study protocol and obtain written consent).

Demographic data, patients' medical history and lab tests are obtained from the anesthesia record and the ICU chart as appropriate. The study protocol does not require any additional tests besides medically indicated by the physicians in charge of the patients.

6.4.2 VISIT 2 - MEDICAL AND STUDY MEASUREMENT

6.4.2.1 PATIENTS CURRENTLY ON OR SCHEDULED FOR VENTILATOR CARE IN THE ICU

The physicians responsible for the patients' medical care will inform the study team when the actual medical intervention is planned. Study team will re-evaluate whether all in- and exclusion criteria are appropriately met (e.g. still intubated).

Study team will setup the investigational devices at least 30 minutes before the medical intervention to allow for stable baseline readings and uninterrupted medical care. PulmoVista 500 electrode belt is placed around the patient's chest, and the PulmoVista 500 is connected to the ventilator. Continuous recording of data is started and verified.

During the investigational phase, the study device will continuously record all data. Before the study measurement, the study team will record baseline readings for at least 5 minutes. During the study measurement, recording will continue uninterrupted; exact time points of events (e.g. when vent settings are adjusted) and details of the study measurement (e.g. old and new vent settings) are recorded by the study personnel according to the clock in PulmoVista 500 (to ensure accurate timing with the recorded data). Recording of the data will continue for at least 5 minutes after the medical intervention is completed.

Once the recording is completed, electrode belt will be removed from the patient and the investigational device will be disconnected.

6.4.2.2 PATIENTS SCHEDULED FOR ELECTIVE SURGERY WITH OLV

Patients scheduled for elective surgery will receive medical care according to the hospital's established standards. Before anesthesia induction, study team will re-evaluate whether all in- and exclusion criteria are appropriately met (e.g. still intubated). Patients are considered "enrolled" when written informed consent has been obtained and all in- and exclusion criteria are appropriately met.

After arrival in the induction room, patients will be connected to the appropriate monitors for routine patient care. Additionally, patients will be asked to sit up and have the electrode belt of PulmoVista 500 fitted to their thorax according to the IfU. Investigational device is set up and connected to the patient and related devices.

Before and during pre-oxygenation of the patient, study personnel will start and test recording of the data. Anesthesia induction, placement and confirmation of correct placement of the DLT / bronchial blocker will be performed according to the hospital's established standards of care.

In patients who require independent lung ventilation during their surgical procedure, EIT measurements shall be performed during normal (both lungs) and single-lung ventilation after induction of anesthesia before start of surgery. According to standard of care correct positioning of the DLT respectively of the bronchial blocker will be tested by switching between normal ventilation and single-lung ventilation (right and left lung will be tested independently).

During the anesthesia induction, study personnel will note the time of particular events (e.g. start of induction, mask ventilation, intubation, clamping left/right) by using the clock on PulmoVista 500. The physician in charge of the anesthesia will be asked to allow uninterrupted baseline readings of at least 2 minutes after successful intubation and to keep the left and right lumen of the DLT clamped for at least 1 minutes each to ensure stable recording of the data. Each step of the testing of correct placement of the DLT or the bronchial blocker will be marked in PulmoVista 500 before the conduct of this step.

Once data have been completely recorded and anesthesia induction is completed, the physician in charge will record approx. 2 minutes and stop the recording afterwards. The electrode belt will then be disconnected from the patient. This concludes the study for this particular patient. Typically, the patient is now transported to the operating room for their surgical procedure; this is not part of the study protocol.

6.4.3 GENERAL

In both cases, if the physicians responsible for the medical care of the patient decide that the data recording for the study purpose interferes with necessary medical care (e.g. in case of cardiac arrest), the data recording will immediately be stopped, the electrode belt removed and every effort will be undertaken to not interfere with the medical care. In this case, the patient will be considered a drop-out.

All obtained data were recorded immediately in the eCRF provided by the KKS Dresden or were transferred to the KKS cloud.

Electronic data of EIT, CT-, MRI-images, ultrasound assessments and radiographs, only marked with the subject identification number, will also be transferred to the KKS cloud. These data were not taken especially for this study, but due to necessary medical treatment. They will be used within this study if they were taken during the period of day -2 to +3.

6.4.4 VISIT 3 - FOLLOW-UP-VISIT

All patients who underwent data recording will be followed up once within 1-3 days after visit 2. During this follow up visit, patients will be asked about any adverse events, and the patients' thorax will be visually inspected for any irritation caused by the electrode belt. If patients are not able to answer (e.g. still sedated or unconscious), the physicians taking care of the patient are questioned about any adverse events.

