4 RISKS AND BENEFITS OF THE INVESTIGATIONAL DEVICE AND CLINICAL INVESTIGATION

4.1 ANTICIPATED CLINICAL BENEFIT AND ANTICIPATED ADVERSE DEVICE EFFECTS

Anticipated clinical benefit:

By participating in the clinical study, the patient benefits of a close monitoring as part of the study, which goes beyond the clinical routine.

Anticipated adverse device effects:

The use of the device according to the normal conditions of use, may cause skin irritation to the patient or pressure marks caused by the electrode belt.

4.2 RESIDUAL RISKS ASSOCIATED WITH THE INVESTIGATIONAL DEVICE, AS IDENTIFIED IN THE RISK ANALYSIS REPORT

Residual Risk associated with the Investigation Device:

PulmoVista 500 is a CE released class IIa medical device. According to the risk analysis for the conformity assessment according to the ISO 14971 there exists no unacceptable individual or overall residual risk for the medical device.

Risks associated with participating in the clinical trial:

Since the study is a non-interventional observational study without additional study-related changes in the treatment of patients, no additional study risks occur through the participation in this clinical study.

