4.4 PROCEDURE TO REDUCE RISKS

As described in the instructions for use of the device the patient's skin should be checked periodically for any discomfort or injury.

In case of intolerance reactions, signs of progressive infection, skin reactions or mechanical irritation, which go beyond the usual extent, the measurement is interrupted and an adequate therapy initiated. The patient will be requested to report problems immediately to the investigator.

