6.1.2 BLINDING

This is an observational trial of intraindividual correlation between two methods of measurement. Since we do not allocate patients to treatment and placebo groups as it would be the case in a randomized trial, blinding is not strictly necessary. However, patients will be blinded to the results of the investigational EIT device by either a) being sedated in the ICU or under general anesthesia or b) device will not be facing them so they cannot see the results.

Study personnel at bedside will not be blinded as they have to interact with the device (to ensure quality of data recording) and therefore blinding is not feasible.

The medical personal responsible for the patient's medical care does not use the information given by the PulmoVista 500 .

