16.4 LIST OF FORESEEABLE ADVERSE EVENTS AND ANTICIPATED ADVERSE DEVICE EFFECTS

It is conceivable that the reusable electrode belt of the PulmoVista 500 carries pathogens from one patient to another, causing infections in a study patient. In order to minimize this risk, we a) exclude any patients with multiresistant pathogens that require isolation of the patient (e.g. MRSA) and b) establish a standardized protocol for proper disinfection of the electrode belt after each use according to the IfU.

The electrode belt consists of a silicone belt with embedded carbonized silicone electrodes. The electrodes shall be coated with a conductive gel before each use to improve coupling with the patient's skin (similar to the procedure during EEG recordings). The belt and the gel could potentially cause mechanical and chemical irritation of the patient's skin. During pre- and post-marketing surveillance of the product, Dräger has never encountered such an event, so we consider this risk to be negligible.

As the study device is CE certified, the sponsor has conducted intensive risk analysis procedures.

The official risk management report concluded that no unacceptable individual or overall residual risk while using the device is existing.

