3 VARIABLE IN THE ANALYSIS

3.1 DEMOGRAPHY AND BASELINE CHARACTERISTICS

The following demographic variables are recorded and evaluated: age and gender. It also detects whether a (pseudo) allergy to silicone or sweat is present. Concomitant diseases are recorded and listed.

Physical features such as height, weight, BMI, chest circumference on day 1 and vital signs (systolic and diastolic blood pressure, heart rate) are displayed with mean and standard deviation.

If necessary, systolic and diastolic blood pressure and heart rate are recorded and displayed on the following day.

Problems with skin before applying the belt are detected.

The characteristic "one-lung ventilation patient" (OLV) or not (ICU) is recorded and evaluated.

If applicable, it is additionally subdivided into Double Lumen Tube (DLT) / Bronchus Blocker (BB) or others.

Electrode belt details such as size, closure position (plughole), belt application in accordance with the clinical investigation plan, electrode mode and signal quality are recorded.

The reasons, why the intervention or surgical procedure has to be done are listed separately according to OLV and ICU group.

The baseline parameters also include the basic data of the ventilation procedure, such as saturation of s_aO_2 , s_pO_2 , p_aO_2 , p_aCO_2 , FiO_2 before and after the intervention. Depending on the distribution, they are determined as mean and standard deviation or as median and percentiles.

If present, auscultation findings, imaging findings (CT, X-ray, or ultrasound) before and after the intervention and the radiological findings are recorded and listed. These findings were collected for the duration of the study (day -2 - day +3).

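### No skin inspection is specified at belt removal; the only dated one is 1–3 days later, after surgery in OLV patients, so short-lived belt effects may be under-recorded and OLV findings are hard to attribute

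*Protocol*

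**What the plan says.** **Anticipated effects.** Protocol 4.1 says that normal use of the device "may cause skin irritation to the patient or pressure marks caused by the electrode belt". Section 4.3 repeats this, and 4.1 lists no other device effect. Section 16.4 adds cross-infection through the reusable belt as conceivable and says of skin irritation that "Dräger has never encountered such an event, so we consider this risk to be negligible".

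**Before the belt.** SAP 3.1 includes a baseline item: "Problems with skin before applying the belt are detected".

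**During wear.** Protocol 4.4 refers to the instructions for use for periodic skin checks. It has the measurement interrupted for reactions beyond what is customary, and adds: "The patient will be requested to report problems immediately to the investigator".

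**At removal, ICU patients (6.4.2.1).** "Once the recording is completed, electrode belt will be removed from the patient and the investigational device will be disconnected". Nothing about the skin follows.

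**At removal, OLV patients (6.4.2.2).** The belt is disconnected once induction and recording are complete. The text then says that the study is over for that patient and continues: "Typically, the patient is now transported to the operating room for their surgical procedure; this is not part of the study protocol".

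**After.** Section 6.4.4 has every patient with a recording seen once, one to three days after Visit 2. At that visit "the patients' thorax will be visually inspected for any irritation caused by the electrode belt". If the patient cannot answer questions, the treating physicians are asked about adverse events.

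**Recording and analysis.** Protocol 14.2 and SAP 5.6.2.1 collect adverse events from enrollment, with onset, end and causal relationship to device and procedures. SAP 5.6.2.1 lists these events in the report. The SAP names no post-belt skin variable.

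**The concern.** Documentation of safety events related to the device is a secondary endpoint, and skin effects are what the plan itself expects to see. The moment when the whole contact area is first exposed is belt removal, and the text asks nobody to look then. The dated inspection comes later, and in OLV patients an operation lies in between.

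Two things are at stake. First, a mark present at removal but gone by Visit 3 enters the data only if someone happens to notice it and opens an adverse-event form. Second, for a chest-wall finding at Visit 3 in an OLV patient, the investigator must judge belt against operation without knowing how the skin looked between the two. A low or zero count could then be read as support for the view in 16.4 that the risk is negligible, although the inspection was not well placed to test it. Section 3.2 says that the data are also meant to support authorization in other countries, so the reading of a zero count matters.

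**Working it through.** The documents give no figure for skin effects, so the check is mainly a comparison of sections.

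**1. When is the skin looked at, and is it recorded?**

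| Time | Source | Skin check written? | Dedicated record? |
|---|---|---|---|
| Before belt | SAP 3.1 | Yes | Yes (baseline variable) |
| During wear | Protocol 4.4 | Yes, periodic, no time points | None stated; an untoward finding goes to the AE form |
| Belt removal, ICU | Protocol 6.4.2.1 | No | No |
| Belt removal, OLV | Protocol 6.4.2.2 | No | No |
| 1–3 days later | Protocol 6.4.4 | Yes | No separate variable in the SAP; AE listing |

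The first half of a before/after comparison is collected. The second half is not, at the time when it would say most about the belt.

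**2. Who has surgery between removal and inspection?** Protocol 6.3.6 plans 80 patients with at least 25 OLV, and 7.7 describes the OLV group as having thoracic surgery: 25/80 = 31%. For the remaining 80 − 25 = 55 or so ICU patients, the documents describe no operation in that interval. For them the issue is delay only.

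**3. Can patient reporting fill the gap?** Section 6.1.2 keeps patients unaware of the results either through "being sedated in the ICU or under general anesthesia" or by turning the screen away. The first group cannot report during wear. The second group may be able to, and 6.3.3 includes spontaneous breathing trials and weaning. Reporting is therefore partial.

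**4. What would a zero count mean?** With 0 events in N patients, the exact two-sided 95% upper limit is 1 − 0.025^(1/N):

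- N = 80: 4.5%
- N = 55: 6.5%
- N = 25: 13.7%

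These limits apply to effects that can be seen when someone looks. Suppose that a share d of belt effects is still visible at Visit 3 and that nothing is captured earlier. The limit for effects present at removal is then the figure above divided by d. The documents do not give d. As an illustration with N = 80:

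- d = 1: 4.5%
- d = 0.5: 4.5/0.5 = 9.0%
- d = 0.25: 4.5/0.25 = 18.0%

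Capture during wear would pull these figures back towards 4.5%. How far cannot be stated, because the periodic check leaves no record of negative findings.

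**The case against.** A reader might infer that the trial cannot see transient belt effects at all and cannot attribute later ones. The documents do not support that. Section 4.4 calls for checks during use. Adverse-event collection runs from enrollment, so it covers wear and removal. A reaction found at a periodic check can meet the definition in 14.1 and must then be entered. The form asks for onset and causality, and a pre-belt skin status exists. Capture is possible but unsystematic, and attribution in OLV patients is weakened rather than lost.

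Three further points stand:

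- Table 1 shows no skin item at Visit 2, but it also omits the EIT measurement and the Visit 3 inspection. Its silence proves nothing. The eCRF is not among the documents, so the claim can only be that no check at removal is written in the protocol or SAP.
- A reader might see a contradiction between 4.1 and 16.4. Section 16.4 also accepts that belt and gel could irritate the skin and then rates the risk as negligible. The emphasis differs, but there is no clear conflict.
- Exposure in OLV patients is probably short, since the belt is worn only from the induction room to the end of induction. Eight hours is a maximum, not a typical duration.

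It can also be argued that the endpoint is documentation only, for a CE-marked device, and that irritation persisting to Visit 3 is what matters. That is a defensible priority, but it does not remove the gap. An adverse-event window is not an assessment, and the interruption rule in 4.4 leaves ordinary marks without any trigger for recording.

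**Conclusion.** The point holds as an inexpensive improvement to the safety assessment. No skin inspection is specified at belt removal for any of the 80 planned patients. The only dated post-belt inspection is one to three days later and, in at least 25 of 80 (31%), after surgery. Short-lived effects may be under-recorded in both groups. The difficulty of separating belt from operation concerns the OLV group only.

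The conclusion rests on one assumption, that some marks fade before Visit 3, for which the documents give no duration. The attribution problem in OLV patients does not depend on it. The primary endpoint is unaffected.

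One related inconsistency is real. Section 6.4.2.2 declares the study finished for the OLV patient at belt removal, while 6.4.4 requires a follow-up visit for everyone with a recording.

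**What to change.** - **Protocol 6.4.2.1, the end of 6.4.2.2, and the Visit 2 schedule:** the person removing the belt looks at the skin under the belt and the reference electrode and records none, mark or irritation in one eCRF field.
- **SAP 5.6.2:** report this finding descriptively as n/N by group, optionally with an exact 95% confidence interval, against the pre-belt skin entry from SAP 3.1. Show the Visit 3 finding beside it as persistence. No hypothesis is needed.
- **Protocol 6.4.2.2 and 6.4.4:** reconcile the statement that the study ends at belt removal with the Visit 3 requirement.

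The cost is one eCRF field and a brief look by staff already at the bedside, with no added procedure for the patient. The downside is that mild, transient marks will now be counted. The report should therefore keep marks and irritation apart.
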